11.2 Relationship to study drug

The following relationships to study drug will be used in the study. Events classified as possible, probable, or definitely will be considered related to study drug.

Not related:

The event does not follow a plausible chronological sequence relative to trial medication administration and can be clearly assigned to other factors, such as patient's clinical condition, therapeutic procedures or administration of concomitant medications.

Possible:

There is sufficient information to accept the possibility of a causal relationship, although the connection is uncertain or doubtful, i.e. causal relationship is not impossible and not unlikely. The event follows a plausible chronological sequence relative to trial medication administration and/or presents the usual response to the drug tested. The event might also be caused by other factors, such as the patient's clinical condition, therapeutic procedures or administration of concomitant medications.

Probable:

There are good reasons and sufficient documentation to assume a causal relationship in the sense of plausible, conceivable, likely, but not necessarily highly probable. The event follows a plausible chronological sequence relative to trial medication administration and/or presents an unexpected response to the trial drug and cannot reasonably be explained by other factors, such as the patient's clinical condition, therapeutic procedures or administration of concomitant medications.

Definitely:

When the event cannot be attributed to the patient's underlying medical condition or other concomitant therapy and there is compelling temporal relationship between the onset of the event and the study investigational product administration that leads the PI to believe there is evidence of a reasonable causal relationship.

11.3 Recording Adverse Events

Each patient will be questioned about AEs at each clinic visit/ following initiation of treatment. The question asked will be "Since your last clinic visit have you had any health problems?" The information can also be obtained from signs and symptoms detected during each examination, observed by the study personnel or spontaneous reports from the study patients or by lab results.

The investigator is to record in the CRFs all directly observed AEs, all AEs as a response of the open question and all AEs spontaneously reported by the patient during the study.

The investigator will record all AEs by:

- Description of event (recorded in standard medical terminology and avoiding abbreviations),
- Start and end date,
- Intensity* (mild, moderate or severe),
- Seriousness (serious or not serious, according to definition),
- Causal relationship, (definitely, possible, probable, unrelated)
- Action taken, (none, treatment required, patient withdrawn, other)
- Outcome of the AE (recovered, recovered with sequelae, death, not recovered)

The Sponsor or delegate will code all AEs and SAEs using MedDRA.

* For each reported AE, the intensity will be recorded. The following definitions of intensity are to be used:

- Mild: A mild AE means awareness of symptoms or signs, but easily tolerated (acceptable).
- Moderate: A moderate AE means enough discomfort to interfere with usual activity (disturbing).
- Severe: A severe AE means incapacity to work or to do usual activity (unacceptable)

If the intensity changes within 24 hours the maximum intensity should be recorded. If the intensity changes over a longer period of time, the changes should be recorded in the CRF.

11.4 Reporting Adverse Events

Adverse Event reporting on each patient shall start at the initiation of study treatment. The reporting shall continue during the course of the study. Spontaneously reported events by study patients in between planned visits shall also be reported. Adverse Drug Reactions, which are unresolved at the time of the last follow-up visit should be followed until the event has resolved or, if persistent, has been assessed as "chronic" or "stable". AEs should be reported for all patients, independent of treatment assignment.

NON-SERIOUS AEs are to be reported in the CRF.

SAEs are to be reported by the investigator to ProductLife Department via the form in the eCRF or via fax ([name]) or email ([contact]).

In case of any question related to SAE reporting please contact Drug Safety Physician/Medical Monitor, see contact information in Table 1. The initial SAE form (provided in the eCRF and in the Investigational Site File (ISF)) should be completed within 24 hours of awareness of the event. All SAEs must be reported whether or not considered drug related. SAEs should also be reported in the CRF.

Completed Serious Adverse Event Reports should be submitted to ProductLife Pharmacovigilance Department within 24 hours of awareness by eCRF, fax ([contact]) or email ([contact]).

After receipt of the initial report, ProductLife Pharmacovigilance Department will forward the information to OxThera. Timelines for reporting and forwarding information are detailed in the Safety Management Plan. ProductLife Pharmacovigilance Department will work with OxThera to review the information received and contact the site to request any missing information/amendments needed. When follow-up information is obtained by the investigator it should also be forwarded to the Medical Monitor within 24 hours. The report should be marked "Follow-up report". Any follow-up received should be treated in the same way as initial reports.

The investigator will submit copies of SAE reports to the independent ethics committee concerned as required by local regulations. All serious and unexpected adverse events will be reported to the European authorities as per regulations.

An Unexpected Adverse Reaction is any adverse reaction, the specificity or severity of which is not specified in the current Investigator's Brochure for the study drug.

A SUSAR is a Suspected Unexpected Serious Adverse Reaction. All SUSARs that are possibly, probably or definitely related to OC5 are subject to expedited reporting to Regulatory Authorities, Ethic Committees and participating investigators in accordance with local requirements in force and the ICH guidelines for Good Clinical Practice (GCP) and the EU Directive 2001/20/EC. ProductLife Pharmacovigilance Department will be responsible for ensuring expedited reporting of SUSARs.

The investigator is responsible for ensuring that there are procedures and expertise available to handle emergencies during the study.

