¹ After the post-treatment period, patients will be offered continuous treatment for 36 months or until transplantation.² Speckle Tracking/Traditional Echocardiography should be done at screening visit +/- 1 month.**Figure 7: Study design for OC5-OL-01 continued treatment period Year 1 and 2**

	Continued Treatment Period Year 1 and 2									
Week	0	4 ¹	8	12	16	20	24	28	32 ²	
Clinic visit	X	X	X	X	X	X	X	X	X	X
Plasma oxalate	X	X	X	X	X	X	X	X	X	X
STE	X ³						X ⁴			
Stool	X	X	X	X	X	X	X	X		X
Safety labs	X	X	X	X	S	X	X	X	X	X

¹ Visit week 4 will be scheduled 28 days (+/- 3 days) after first day of continued treatment after study week 14.² Treatment Year 1 and 2 will continue with the same frequency of visits and collections until week 104 or until the patient is transplanted. Visit intervals and examinations/samplings will be kept the same throughout year 1 and 2 of the continued treatment period.³ For patients who did not have a Speckle Tracking/Traditional Echocardiography performed at screening, an effort will be made to perform this examination before start of continued treatment.⁴ Speckle Tracking/Traditional Echocardiography will be repeated every 6th month during year 1 and 2 of the continued treatment period in weeks 0, 24, 48, 72 and 104.

Figure 8: Study design for OC5-OL-01 continued treatment period Year 3

Continued Treatment Period Year 3				
Week	116	128	140	156
Clinic visit	X	X	X	X
Plasma oxalate	X	X	X	X
STE ¹		X		X
Stool	X	X	X	X
Safety labs	X	X	X	X

¹ Speckle Tracking/Traditional Echocardiography will be repeated every 6th month during the continued treatment period year 3, in weeks 128 and 156.

Faecal samples will be collected for determination of *O. formigenes* at weeks 4, 10, 14, every 2 months throughout the first 24 months of the continued treatment period and every 3-4 months for the last 12 months of the continued treatment period. Faeces samples will be analysed at Institut fur Mikroökologie in Herborn, Germany.

Safety evaluation will include safety labs at weeks 0, 4, 10, 14, monthly throughout the first 24 months of the continued treatment period and every 3-4 months for the last 12 months of the continued treatment period. Physical examination will be done at weeks 0, 4, 10, 14, every second month during continued treatment year 1 and 2 and every 3-4 months during continued treatment year 3. Adverse events will be monitored throughout the study. Specimen samples will be analysed at a local laboratory.

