For the course of the study, the patients should be instructed to maintain their normal diet and fluid intake as prescribed under their standard clinical care.

All patients will be monitored for safety and concomitant medication usage throughout the study period.

Monitoring of adverse events, concomitant medication and compliance with the administration of study drug will be performed at least once monthly at each study visit for the first two years of continued treatment and at least every 3-4 months during the last year of the continued treatment period.

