Faeces: The measurement at week 4 is considered the baseline value.

Echography: The screening value is used as baseline. If this value is missing, the CT week 0 value is used as baseline value instead.

Safety lab: Safety lab is determined at screening and at week 4. The week 4 measurement is considered the baseline value. If this value is missing, the screening value will be used instead.

Data for screening failures will not be presented in summary tables, except for disposition and end-of-study displays, provided end-of-study data includes screen failures. Data for screening failures will be listed as available.

For this study, a treatment emergent adverse event (TEAE) is defined as an adverse event reported on or after first dose of study treatment. AEs after last dose date, and thus also after study drop-out, are not collected.

All descriptive statistics tables will be presenting data per visit, if applicable.

Any statistical significance determined in the analyses will be viewed with caution, considering the very small and heterogeneous patient population. Any determined p-values can only be indicative. No correction for multiple comparisons will be applied for any of the endpoints.

All collected data will be presented as is in individual data listings, and no other (calculated) data will be added unless specifically specified in the respective section. In case derived variables are to be added to the listings, both the original variable as well as the derived will be presented. For all relevant listings, study day will be added. The calculation for this day is as described in section 9.1.

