6.7.1 Adverse events

Treatment emergent adverse events (TEAE) are defined as adverse events reported on or after first dose of study treatment. AEs after last dose date, and thus also after study drop-out, are not collected. All AEs reported in the study will be listed.

An AE overview table will be created displaying the number of patients (and percentage) experiencing a treatment-emergent adverse event (TEAE) and the number of TEAEs for: any TEAE, any mild/moderate/severe TEAE, any related/unrelated TEAE, any SAE, any Fatal AEs/Deaths during study and any TEAE leading to study discontinuation. Unique adverse events are determined based on System Organ Class (SOC) and Preferred Term (PT).

All TEAEs are tabulated by SOC and PT within each SOC according to the MedDRA terminology list. TEAEs will also be tabulated by intensity (mild/moderate/severe) and by relationship to study medication (related/unrelated), using frequency counts (number of patients with at least one event, and number of events) and percentage of patients with the event. Similar tables will be created for TEAEs leading to premature discontinuation, SAEs and fatal AEs/deaths, if applicable. In addition, a summary table will be created for TEAEs by intensity and relationship with the IMP including patient identification. All summary tables will be presented by decreasing frequency of occurrence based on SOC and PT.

The summary tables will be accompanied by individual subject listings of *all* reported AEs including information on AE number, actual AE description, date/time of start and end of AE (or ongoing), treatment-emergent (as in: present to first dose), PT (MedDRA), SOC (MedDRA), intensity, relationship, seriousness, action taken and outcome. Pre-existing AEs are not considered to be treatment-emergent, except in case of worsening during/after study treatment (to be collected as separate AE in the database). AEs starting prior to administration of the study drug will only be listed. In this listing, a clear distinction will be made between prior and treatment emergent events.

Separate listings will be created for SAEs and deaths, if applicable.

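### No adverse events are scheduled for collection in the untreated run-in, and the SAP defines treatment-emergent events by report date in one rule and by onset in another

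*Protocol*

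**What the plan says.** **Start of collection.** Protocol 11.4: "Adverse Event reporting on each patient shall start at the initiation of study treatment". Protocol 11.3: "Each patient will be questioned about AEs at each clinic visit/ following initiation of treatment". The AE row of Protocol Table 4 is marked at weeks 6, 8, 10, 12 and 14. Section 6.2.2 (Baseline) lists plasma oxalate, safety labs, faeces, medication changes and an eligibility review for the week 2 and week 4 visits, but no AE assessment.

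**Statements pointing the other way.** The synopsis and Protocol 6.1 say "Adverse events will be monitored throughout the study". Section 6.1 adds "All patients will be monitored for safety and concomitant medication usage throughout the study period".

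**What is recorded for each AE.** Protocol 11.3 includes "Start and end date" among the fields. The question put to the patient is "Since your last clinic visit have you had any health problems".

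**SAP rules.** SAP 6.1 states that "a treatment emergent adverse event (TEAE) is defined as an adverse event reported on or after first dose of study treatment", and 6.7.1 repeats the definition. SAP 6.7.1 also says "AEs starting prior to administration of the study drug will only be listed", promises that the listing will separate prior from treatment-emergent events, and counts a pre-existing AE as treatment-emergent only if it worsens. SAP 6.1, 6.7.1 and 7 say that AEs after the last dose are not collected.

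**The concern.** The study is open-label with no comparator, in dialysis patients with end-stage renal disease, most of them on a transplant waiting list (Protocol 11.5.1.2). Their background rate of events is likely to be high, though the documents give no figure. The four weeks before first dose show each patient's background before any exposure to the drug. Nobody is scheduled to ask about AEs in that time.

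Two things follow. First, the AE tables will have no run-in rate beside them, and the SAP's worsening rule will have little record of the state from which an event worsened. Second, the SAP has two rules for the same classification. Because AE reporting starts only at first dose, every recorded AE is treatment-emergent under the report-date rule, which leaves the prior category with no members. Under the onset rule, an event that began before first dose is prior. The programmer has to choose between them, and the choice changes the TEAE tables.

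**Working it through.** The plan states no AE rate and no sample-size calculation, so there is no figure to reproduce. The check counts visits and patient-time, then applies the SAP rules to specific cases.

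**1. AE assessments in Protocol Table 4**

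| Period | Visits | With AE assessment |
|---|---|---|
| Before first dose | Screening, weeks 2 and 4 | 0 of 3 |
| After first dose | Weeks 6, 8, 10, 12 and 14 | 5 of 5 |

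**2. Patient-time.** Inputs: 12 patients dosed and 8 entered continued treatment (Protocol 11.5.1.2); run-in 4 weeks, first course 6 weeks, off-drug 4 weeks (synopsis). Full attendance is assumed.

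- Run-in: 12 × 4 = 48 patient-weeks, with no AE collection scheduled. Screening of up to 4 weeks could add up to 48 more.
- First course: 12 × 6 = 72 patient-weeks.
- Weeks 11 to 14: 12 × 4 = 48 patient-weeks. Of these, 8 × 4 = 32 belong to patients who went on to further dosing and (12 − 8) × 4 = 16 to patients who did not.

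For those four patients, weeks 11 to 14 follow their last dose. The SAP says such AEs are not collected; Protocol 6.2.4 assesses AEs at weeks 12 and 14. So at least 16 of the 48 off-drug patient-weeks are in doubt.

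**3. The two SAP rules applied to the same event**

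| Event, as recorded | By report date (6.1, 6.7.1) | By onset (6.7.1) |
|---|---|---|
| Starts after the week 4 visit but before first dose; mentioned at week 6 | TEAE | Prior, listed only |
| Starts earlier in the run-in, persists; volunteered at week 6 | TEAE | Prior, listed only |
| Starts after first dose | TEAE | TEAE |

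The first row is within the plan's own procedure, because the week 6 question reaches back to the week 4 visit. The documents do not give the interval between that visit and first dose. The second row lies outside the recall window and depends on the patient raising it.

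SAP 6.2 adds to this. If an event continues past first dose and its start day is missing in the month of first dose, or its start date is wholly missing, the start is set to the first dose date. That is conservative, but there are no scheduled run-in AE records to check it against.

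**4. What run-in data could have shown.** With zero events in 48 patient-weeks, the one-sided 95% upper limit is −ln(0.05)/48 = 0.062 per patient-week, about 3.3 per patient-year.

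For a comparison of run-in with first course, conditional on the total number of events, the on-drug share is 72/(48 + 72) = 0.60 if rates are equal. It is 144/(48 + 144) = 0.75 if the rate doubles and 216/(48 + 216) = 0.82 if it triples. *Assumption, not in the documents:* background of 0.25, 0.5 or 1 event per patient per 4 weeks (3, 6 or 12 expected run-in events), independent Poisson events, one-sided 0.05.

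| Background per patient per 4 weeks | Power, doubled rate | Power, tripled rate |
|---|---|---|
| 0.25 | 19% | 50% |
| 0.5 | 36% | 82% |
| 1 | 65% | 98% |

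So run-in data would mainly give descriptive context and correct onset classification.

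**The case against.** The best defence has four parts.

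- **The split can be made.** A reader might infer that prior and treatment-emergent events cannot be separated at all. The documents do not support that: onset dates are recorded, SAP 6.2 handles missing ones, and SAP 6.7.1 already keeps pre-dose onsets out of the summary tables. This stands. What remains is that the prior category will be nearly empty and that the stated TEAE definition contradicts the onset rule.
- **The run-in leaves traces.** A reader might infer that run-in events are recorded nowhere. That is also too strong. Medication changes are recorded at weeks 2 and 4, and the SAP 6.7.4 listing shows whether a drug was given for an AE. Labs and physical examination are repeated at week 4, medical history with symptoms is taken at screening, and Protocol 13 expects medical records to hold any AEs and SAEs. This stands, but none of it gives an AE rate.
- **Starting at first dose is a coherent choice.** Protocol 11.1 defines an AE in a patient given a product. That supports 11.4, but not the wording in the synopsis and 6.1, nor an SAP written as if prior AEs would be on file.
- **It is late.** The planned maximum of 12 patients has been dosed and one remained in the study in September 2019. Prospective capture would help only further patients, whom Protocol 7.3 allows at the sponsor's discretion. This stands and shapes the fix.

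**Conclusion.** The point holds in this form: no AE or SAE collection is scheduled before first dose, against the protocol's own statements of monitoring for the whole study, and the SAP's TEAE definition conflicts with its onset rule. The size is 0 of 3 pre-dose visits and 48 run-in patient-weeks without an AE rate (12 patients, 4 weeks each), beside 72 on drug in the first course.

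The documents do not show how many events would change class. That depends on how many began before first dose and were reported later, and it may be few.

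A reader might also infer a definite gain in precision for an on-drug versus off-drug rate ratio. That is not supported. No such analysis is planned (SAP 6.1 calls the evaluations explorative), no background rate is given, and the off-drug weeks 11 to 14 are themselves in doubt for at least 16 patient-weeks. The case rests on the contradictory definitions and the missing descriptive context, and these are worth correcting because the correction is cheap.

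**What to change.** 1. **SAP 6.1 and 6.7.1, both places:** define a TEAE as an AE with onset, or worsening of a pre-existing event, on or after first dose, and remove the report-date criterion. Changing one section alone leaves the contradiction. Cost: wording only.
2. **Protocol 11.3, 11.4 and Table 4:** reconcile with the synopsis and 6.1. For any patient still to be enrolled, record AEs and SAEs from consent and put the AE question at the existing week 2 and week 4 visits. SAP Table 1 should follow. Cost: an amendment and a few extra AE pages, with no added visits.
3. **The 12 patients already dosed:** list run-in events found in the medical records, flagged as retrospective. Use them only to identify pre-existing conditions. Do not set them beside on-drug events in a rate table: chart-abstracted events are less complete than questioned ones, so the comparison would tend to make the drug look worse. Downside: the abstraction takes site time and will be incomplete.
4. **Study report:** state that no run-in AE rate exists.
5. **AEs after last dose:** reconcile the SAP statement that these are not collected with the protocol's assessments at weeks 12 and 14, and say what last dose means for patients who continue. Do this before using weeks 11 to 14 as an off-drug comparator.

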11.5 Anticipated Adverse Events

11.5.1 Review of available data

OC3 has been evaluated in several clinical studies in patients with PH; one 28-day phase I/II study (OC3a), one 24-week double blind placebo-controlled multicentre international phase II/III clinical study including a 24-week open-label extension study (OC3b), and one 24-week double-blind placebo-controlled multicentre international phase II/III clinical study (OC3b buffer formulation), see Table 3. OC5 has been evaluated in one completed double-blind placebo-controlled multicentre international phase II study, the current ongoing phase II open-label study, and two ongoing phase III trials, see Table 3. In summary OC3 and OC5 have been evaluated in over 100 subjects receiving a dose of up to 10⁹ CFU twice a day. The continuous exposure to study drug ranged from 4 weeks up to 3 years. Both OC3 and OC5 were considered safe and well tolerated in all clinical studies.

Review of the safety data from all the completed studies indicate that patients may experience headache and gastrointestinal symptoms including abdominal pain,

constipation, nausea, vomiting, diarrhoea, and flatulence.

No treatment related serious adverse events for Oxabact® were reported in patients with PH. In all studies, the majority of adverse events were reported as mild and unlikely related to the treatment. In the placebo-controlled studies, the adverse events were equally distributed between Oxabact® and placebo.

As a safety precaution, children were not treated with OC5 in the OC5-OL-01 study until the 4-week safety data from at least two adult patients in the OC5-DB-01 study had been reviewed.

